### **Aim:**

The study evaluated the effect of different doses of metformin on the intermediates of NO (nitric oxide) biosynthesis in people with pre-DM (pre-diabetes).

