4. Baseline parameters collected: weight, height, BMI (body mass index), information about fatty liver (based on the available ultrasonography organs' description), family history for DM (YES/NO), hypertension (YES/NO), active nicotinism (YES/NO); and biochemical: FPG, lipids profile, creatinine, AlaT (alanine transaminase), creatinine, HbA1c (glycated hemoglobin) if available.

5. Before the first dose of the metformin and after: 6, 12, 15 weeks of the treatment, the blood samples were collected for the assessment of the:

a. concentration of the metformin

b. concentration of the compounds related to the production of the NO: L-arginine, L-citrulline, ADMA – asymmetric dimethylarginine, DMA – dimethylamine, SDMA – symmetric dimethylarginine, ornithine

\* For healthy volunteers only once concentration for the compounds related to the production of the NO was assessed and no blood samples for metformin concentration were taken.

The admissible delay in taking blood for lab-testing was set at 4 days. The blood samples were taken randomly (no hours or gaps between metformin taking were defined).

6. Patients with pre-DM were treated 3 weeks with an increasing dose of the immediate-release (regular form) metformin to 3 x 500 mg, and then randomly assigned to:

group A – continuation of a dose of 3 x 500 mg or

group B – increase dose to: 3 x 1000 mg (also by titration); after 12 weeks this group returned to the dose 3 x 500 mg for the next 3 weeks

7. If potential side effects appeared in group B, the patients could take a lower dose (3 x 500 mg if well-tolerated) and thus change to group A.

8. If the smallest dosage (3 x 500mg) was not tolerated the patient was excluded from the study.

9. During titration period (by phone) and blood collection visits (personally), patients were asked about the compliance and drug's tolerance. The patients were also encouraged to contact in any case of the problem with metformin tolerance.

10. The technique used to assess concentration of the metformin in serum and the wider panel of L-arginine/NO pathway metabolites: LC-MS/MS (liquid chromatography-mass spectrometry).

11. Safety outcomes: Adverse events were reported at each clinic visit and revised via telephone contact during treatment period.

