## 12. SAP- Statistical Analysis Plan

- to prove the homogeneity of the compared groups, analysis of the baseline parameters was done
- to show the potential differences between people with pre-DM and healthy people the comparison of the baseline parameters was done
- to follow the metformin intake by the patients, the metformin concentration with its change during the therapy was done
- for the analysis of the impact of the metformin dosage on the concentration of the compounds related to the production of the NO the difference of these compounds between two groups was done
- as an extra analysis, the correlations of the serum drug concentration with BMI and body mass, after 6 and 15 weeks of the treatment was done, while research was ongoing

[figure not shown]
The Statistica 13 program was used with cut-off point for statistical significance (P) at 0.05.

The normality of the distribution of the examined quantitative variables was checked using the Shapiro-Wilk test. In order to determine the significance, statistical tests were used in accordance with the distribution of variables and the nature of the data (Student t test, Welch test, Mann-Whitney test, chi – square test, the Wilcoxon signed-rank test, Kruskal – Wallis test, Friedman test, F test). To determine the correlation the Spearman's rank-order correlation and the Pearson correlation was used.

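### The dose comparison tests six compounds, each at P = 0.05, with no primary compound, visit or multiplicity rule: at week 12 alone the chance of a false dose effect is 26% if the tests are independent and 11% at an assumed correlation of 0.9

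*Combined protocol and SAP*

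**What the plan says.** The Aim reads: "The study evaluated the effect of different doses of metformin on the intermediates of NO (nitric oxide) biosynthesis". Methods item 5 lists six compounds (L-arginine, L-citrulline, ADMA, DMA, SDMA and ornithine) and four sampling times: "Before the first dose of the metformin and after: 6, 12, 15 weeks of the treatment, the blood samples were collected".

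The SAP (item 12) answers the aim in one bullet. For the impact of dosage on these compounds, "the difference of these compounds between two groups was done". The significance rule for every analysis is "The Statistica 13 program was used with cut-off point for statistical significance (P) at 0.05". The tests listed are single-comparison or omnibus tests chosen by distribution, with no multiple-comparison procedure among them.

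The SAP names visits only for an extra analysis, the correlation of drug concentration with BMI and body mass: "after 6 and 15 weeks of the treatment was done, while research was ongoing". It names none for the dose comparison.

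Three design features bear on the count and on the remedy:

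- **Return to the lower dose.** In group B, "after 12 weeks this group returned to the dose 3 x 500 mg for the next 3 weeks" (Methods item 6).
- **Change of group.** If side effects appear in group B, "the patients could take a lower dose (3 x 500 mg if well-tolerated) and thus change to group A" (Methods item 7).
- **Time of randomisation.** Item 6 gives three weeks of increasing dose, "and then randomly assigned to" the two groups. The flow chart places a control visit with blood sampling before randomisation, and six weeks in each group between that visit and the next.

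**The concern.** The aim concerns the intermediates as a set, and nothing ranks one compound above another. Followed as written, the plan allows any one of six results below 0.05 to be reported as an effect of dose. When dose affects none of the compounds, the chance of at least one such result is well above the nominal 5% unless the six test statistics are almost perfectly correlated. Two further choices are open: which visit carries the claim, and whether the difference is in the level or in the change from baseline. Each is another route to a chance finding. What is at stake is whether a reported dose effect on a single compound can be told apart from chance.

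**Working it through.** **Inputs**

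- Per-test threshold 0.05 (SAP, item 12). Sidedness is not stated; two-sided is assumed.
- Six compounds (Methods item 5; flow chart).
- Visit: week 12. Counting weeks from the start of treatment, it is the last sample before group B's dose is reduced (Methods items 5 and 6; flow chart), so six tests is the smallest count that answers the aim.
- Correlation between the six test statistics: not in the documents; a range is shown.
- The plan states no sample size, power or family-wise error, so there is no figure of its own to reproduce first.

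**Step 1. Independent tests.** Chance of at least one false result = 1 − 0.95^6 = 1 − 0.735 = 0.265.

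**Step 2. Correlated tests.** Take six normal test statistics with a common correlation r and no dose effect, and compute 1 − P(all six |Z| ≤ 1.96) by numerical integration:

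| r (assumed) | 0 | 0.3 | 0.5 | 0.7 | 0.9 | 0.95 | 0.99 |
|---|---|---|---|---|---|---|---|
| Chance of at least one false result | 26.5% | 24.1% | 20.7% | 16.4% | 10.8% | 8.9% | 6.6% |

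Simulation with 1,000,000 draws gives 26.5%, 20.8% and 10.9% at r = 0, 0.5 and 0.9.

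**Step 3. Holm at week 12.** The first step is 0.05/6 = 0.0083. With no dose effect on any compound, the error is the chance that the smallest P value falls below this: 1 − (1 − 0.0083)^6 = 4.9% if independent, 4.1% at r = 0.5 and 2.1% at r = 0.9.

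**Step 4. Does Holm suffice if the outcome form stays open?** With independent compounds and an assumed baseline to week-12 correlation of 0.5, allowing either the level or the change to be reported raises the Holm error to about 9%. The rule must therefore fix the outcome form too.

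**Step 5. Power cost.** Two-sample t test, noncentrality d × √(n/2), with n per arm. Both d and n are assumptions:

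| Effect d | n per arm | d × √(n/2) | Power at 0.05 | Power at 0.0083 |
|---|---|---|---|---|
| 0.8 SD | 50 | 4.00 | 98% | 90% |
| 0.5 SD | 50 | 2.50 | 70% | 43% |
| 0.8 SD | 25 | 2.83 | 79% | 53% |
| 0.5 SD | 25 | 1.77 | 41% | 18% |

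For 80% power, n per arm rises from 26 to 40 (0.8 SD) or from 64 to 99 (0.5 SD).

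**The case against.** **The compounds belong to one pathway, so the tests are correlated.** This stands in part. The figure falls with correlation, and 11% is not a floor: it is 8.9% at 0.95 and 6.6% at 0.99. At 0.9 the error is still about twice nominal.

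**This is a small mechanistic study that nobody would read as confirmatory.** The text does not say so. Only the correlation analysis is given lower rank; the dose comparison is the aim itself.

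**A rule may exist in material not seen.** A figure in the SAP section is not shown and some front matter was removed. Nothing readable points to a rule there, but the absence is of readable text only.

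**Holm may be moot.** Recruitment ended in December 2018 and the SAP is in the past tense. This stands: unless prior choice can be shown, only the exploratory label remains.

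Three stronger readings are tempting and are not supported.

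- **Eighteen tests.** A reader might multiply six compounds by three on-treatment visits and infer 1 − 0.95^18 = 60%. That needs week 6 to fall after randomisation. The flow chart puts a control visit before randomisation, and its intervals (six weeks, then three) fit samples at weeks 6, 12 and 15. It also needs week 15, when group B has had three weeks on group A's dose, to be reported as a concurrent dose effect.
- **Week 15 is uninformative.** Also too strong: a difference then between randomised groups could still be an effect of the earlier dose. It answers a different question.
- **Change of group inflates the error by a known amount.** The documents do not say that patients are analysed in the group they moved to, and give no switching rate. Simulated Holm error under that analysis, with 10–20% of group B switching and tolerance correlated 0.2–0.3 with each compound, was 5% to 16% at a compound correlation of 0.3, but only about 3% to 7% at 0.9. The direction of the problem is clear; its size is not.

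**Conclusion.** The point holds for six compounds at week 12. Nothing readable limits the dose claim to one compound, one visit or an adjusted threshold. The resulting chance of a false dose effect is 26% under independence and 24% to 11% at assumed correlations of 0.3 to 0.9, falling to about 7% at 0.99. These figures assume no dose effect on any compound, two-sided tests, normal test statistics and a common correlation; the range is a sensitivity range, not an estimate. An open visit or outcome form can only add to it, by an amount the documents do not fix. This is more than missing detail, because it decides what the trial may conclude, but rewording and re-analysis of existing data correct it.

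**What to change.** 1. **If it can be shown that the rule was set without sight of the compound data:** rest the dose claim on week 12 only. State one outcome form and one test for all six compounds, for example the week-12 value adjusted for the baseline value already collected. Apply Holm across the six, with first step 0.0083. Date the rule.
2. **Analyse patients in the group to which they were randomised**, not the group they moved to under Methods item 7. Moving the less tolerant group B patients into group A is selection that Holm does not correct. Report how many switched, how many were excluded under item 8 after randomisation, and how many lack a week-12 sample.
3. **Otherwise:** label all six comparisons exploratory, report all six with confidence intervals, and claim no proven dose effect. The same applies if Holm is not adopted or the original allocation cannot be recovered. Because the SAP describes the analyses as done, this may be the only option left. Naming one primary compound now would not control the error if data have been seen.
4. **Other visits:** report week 15 separately, as the difference after group B returned to group A's dose. Reconcile the time of randomisation (Methods item 6 against the flow chart) before using week 6 as a dose comparison.

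**Cost.** SAP wording, the allocation list and re-analysis of existing samples. Holm's first step lowers power as tabulated, for example from 70% to 43% at 50 per arm and 0.5 SD. Analysis as randomised dilutes the effect further if patients switch: with an assumed 20% switching and the effect multiplied by 0.8, first-step power at 50 per arm is 69% (0.8 SD) or 25% (0.5 SD). Results already reported at 0.05 may lose significance. The exploratory label costs no power but gives up a confirmatory claim.

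### The dose comparison uses a test chosen by a normality check, gives the pre-dose sample no role, and plans no A-versus-B estimate with a confidence interval

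*Combined protocol and SAP*

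**What the plan says.** Methods, item 5, schedules blood samples "Before the first dose of the metformin and after: 6, 12, 15 weeks of the treatment", which makes four per treated patient, for six compounds: "L-arginine, L-citrulline, ADMA – asymmetric dimethylarginine, DMA – dimethylamine, SDMA – symmetric dimethylarginine, ornithine".

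Section 12 (SAP) covers the effect of dose on these compounds in one clause: "the difference of these compounds between two groups was done". On method it states: "The normality of the distribution of the examined quantitative variables was checked using the Shapiro-Wilk test". It then adds that "statistical tests were used in accordance with the distribution of variables and the nature of the data". The list in brackets has eight tests: Student t, Welch, Mann-Whitney and chi-square, followed by "the Wilcoxon signed-rank test, Kruskal – Wallis test, Friedman test, F test". No test is tied to a compound, a visit or a contrast. The only decision rule is a "cut-off point for statistical significance (P) at 0.05".

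The SAP uses baseline parameters to show that the groups are alike and to compare patients with healthy volunteers. It does not say that a patient's own pre-dose value enters the dose comparison. It mentions no log transformation, effect estimate, confidence interval or handling of missing samples.

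**The concern.** The stated aim is the effect of different doses. That calls for an estimate of how far A and B differ, with its uncertainty, at a time when the assigned doses differ. The SAP would deliver p-values from tests that depend on the data.

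Two things follow. First, a normality check applied variable by variable can send one compound to a comparison of means and the next to a comparison of ranks, so the six results share no effect scale. Second, a two-group test at a single visit treats stable differences between patients as noise. The pre-dose sample would remove part of that noise, and it has already been collected.

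**Working it through.** **Inputs.** From the documents: six compounds, four sampling times, two groups, significance level 0.05. Not in the documents: sample size, SD, correlation between visits, effect size, missing-data rate. There is no planned power figure to reproduce, so everything below rests on assumptions: 25 per arm, log-normal concentrations with log SD 0.2, 0.3 or 0.5, a dose effect of 0.6 log-SD, and correlation ρ between the pre-dose and follow-up values from 0 to 0.6. The assumed effect is an A/B difference of exp(0.6 × 0.2) = 1.13, exp(0.6 × 0.3) = 1.20 or exp(0.6 × 0.5) = 1.35 as a ratio.

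**Step 1: mixing of scales.** In simulation with no dose effect, the check sent the comparison to Mann-Whitney in a share m = 0.29, 0.50 and 0.86 of datasets for log SD 0.2, 0.3 and 0.5. For six independent compounds, the chance that some are tested on means and others on ranks is 1 − m⁶ − (1 − m)⁶:
- log SD 0.2: 1 − 0.29⁶ − 0.71⁶ = 0.87
- log SD 0.3: 1 − 0.50⁶ − 0.50⁶ = 0.97
- log SD 0.5: 1 − 0.86⁶ − 0.14⁶ = 0.60

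Correlation between compounds would lower these figures; different variability between compounds could raise them.

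**Step 2: power, closed form.** Adjusting for the pre-dose value multiplies the residual variance by 1 − ρ². The non-centrality is 0.6 × √(25/2) / √(1 − ρ²) = 2.12 / √(1 − ρ²). Two-sided power at 5% (chance baseline imbalance ignored):

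| ρ | 1 − ρ² | Non-centrality | Power, closed form | Power, simulated |
|---|---|---|---|---|
| 0 | 1.00 | 2.12 | 55% | 53–55% |
| 0.2 | 0.96 | 2.16 | 56% | 55–57% |
| 0.4 | 0.84 | 2.31 | 62% | 60–63% |
| 0.6 | 0.64 | 2.65 | 74% | 73–75% |

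The gated test on follow-up values gave about 53–57%. Type I error was about 5% for both routes. With 3000 runs the Monte Carlo 95% error near 74% is 1.96 × √(0.74 × 0.26 / 3000) = 1.6 points, and repeat runs differed by about that much.

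**Step 3: where the gain comes from.** At ρ = 0.6, for log SD 0.2 / 0.3 / 0.5, one run gave:
- gated test on raw values: 0.543 / 0.533 / 0.525
- unadjusted t test on logs, no gate: 0.542 / 0.545 / 0.544
- baseline-adjusted analysis of raw values: 0.730 / 0.696 / 0.660
- baseline-adjusted analysis of logs: 0.748 / 0.727 / 0.722

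Removing the gate and taking logs changes power by about 0–2 points. Adding the pre-dose value accounts for nearly all the rest.

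**Step 4: the mixed model itself.** Steps 2 and 3 use one follow-up visit. A separate simulation fitted a log-scale random-intercept model to all four visits (25 per arm, log SD 0.25, a 15% effect at week 12 only, 10% of samples missing at random per follow-up visit). Power was 0.54 at correlation 0.4 and 0.77 at 0.7, against 0.46 and 0.53 for the gated week-12 test. With 200 runs the error is about ±7 points, so only the second gap is clear.

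**The case against.** The best defence is that the SAP is terse and need not be read in its weakest form. Its dose clause does not rule out change from baseline. The same gate applied to change scores gave 0.656 / 0.641 / 0.631 at ρ = 0.6, about half the gap closed, although it does worse at low correlation. The listed F test is undefined and could include an analysis of variance. Both points stand. They also show that the analysis is not fixed, which is part of the concern.

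Two stronger readings are tempting, and the documents support neither.

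*A reader might infer that the Shapiro-Wilk check costs about 20 points of power or distorts the error rate.* Step 3 shows that the check costs almost no power, and single-comparison type I error stays near 5%. Its harm is the mixture of effect scales.

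*A reader might infer that the plan discards about a quarter of patients.* Friedman does need every visit: with 10% missing at each of three follow-up visits, 1 − 0.9³ = 27% of patients would drop out (9% at 3% missing, 49% at 20%). These missing rates are assumed. The SAP lists Friedman without assigning it to the serial samples, and used within an arm it does not compare doses. Wilcoxon loses only incomplete pairs, and a two-group test at one visit keeps everyone sampled then.

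It is also fair to say that no model recovers samples never taken from patients excluded for intolerance (Methods, item 8).

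**Conclusion.** The concern holds in a limited form. The SAP pre-specifies no baseline-adjusted A-versus-B estimate with a confidence interval, and it lets the data decide whether each compound is judged on means or ranks. Under the assumed 25 per arm and 0.6 log-SD effect, the precision forgone is worth essentially nothing at correlation 0 to 0.2. It is worth several points of power at 0.4 and close to 20 points at 0.6. The documents do not say where the true correlation lies. The missing estimate and the mixed scales do not depend on these assumptions; only their numerical size does. This is a loss of precision and interpretability, not an inflated false-positive rate for a single comparison.

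**What to change.** **First reconcile the timing of randomisation.** Methods, item 6, places it after 3 weeks of treatment. The flow chart places it after a control visit with samples and shows six weeks in each group before the next control visit. Counting back from week 12, 12 − 6 = 6, which would make week 6 a pre-randomisation value. Until this is settled, week 6 cannot be classed as baseline or outcome.

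**Then pre-specify for each of the six compounds:**
- a linear mixed model on log concentration with randomised group, visit, group-by-visit and the pre-dose value, patient as the repeated unit, using all available samples;
- analysis of every patient in the arm to which they were randomised, including those who move from group B to group A under Methods, item 7;
- the week-12 A/B ratio with 95% confidence interval as the dose estimate, because by week 15 both groups are assigned 3 x 500 mg;
- no Shapiro-Wilk gate for this contrast; a rank-based test as sensitivity analysis; Friedman and Wilcoxon as descriptive within-arm results only.

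**Cost.** SAP wording and a standard model, with no new samples. The SAP is written in the past tense, so in practice this is a re-analysis of stored values. The model relies on approximate log-normality and on data missing at random. It does not remove bias from exclusions for intolerance. It also leaves multiplicity open: six independent tests at 0.05 give a family-wise error of 1 − 0.95⁶ = 26%, so a separate rule across compounds is still needed.

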## The flow chart of the management of the patients

Met “Inclusion criteria”: YES; Written consent: YES

Initial visit: blood samples for: arginine, citrulline, ADMA, DMA, SDMA, ornithine

Control visit: blood samples for: arginine, citrulline, ADMA, DMA, SDMA, ornithine  
and metformin

### Randomization

Group B

*3 weeks titration to the dose:*

*3000mg/day*

Group A

[figure not shown]
*6 weeks continuation of the dose 1500/day*

Good dose tolerance: YES

NO

*3 weeks continuation of the dose*  
*3000mg/day*

Control visit: blood samples for: arginine, citrulline, ADMA, DMA, SDMA, ornithine  
and metformin

*3 weeks continuation of the dose 1500mg/day*

Final visit: blood samples for: arginine, citrulline, ADMA, DMA, SDMA, ornithine  
and metformin
